D5.1 Pre-data collection procedures. During the study team member will inform the candidate that incentives will be given in person and the participant will receive a total of \$75 in physical gift cards for study participation (\$25 for baseline outcome measure completion (Visit 1), \$25 for completion of the 15-20 minute debrief interview (Visit 2), and \$25 for the follow-up data completion at 30-days post-intervention (Visit 3)). If eligible, the study team member will schedule a convenient time to meet with the candidate to complete informed consent prior to data collection, within approximately 14 days of initial contact. During Visit 1: with the participant, electronic consent and any identifier data will be entered directly into REDCap [7]. A signed consent copy will be given to the participant. A unique study ID will be created for the questionnaire procedures and kept separate from any participant identifiers. Consent procedures will take

previous research success with this community enable a **rigorous approach that will enable completion of all study activities within the 12-month funding period.**

D7. Instruments and variables.

Validated measures will be used for Aim 1 and the quantitative portion of Aim 2 [28-30]. Background characteristics will include demographics, social determinants of health (PRAPARE-18) [31], Health Literacy (BHLS-3) [32], and anxiety/depression (PHQ-4) [33]. Intervention variables that will be used to shape the TIC adaptation include adverse childhood experiences (ACE-10) [34] and death-related experiences (6 items) [35]. All variables were selected per the relevant ACP, TIC, and Implementation Science literature [23, 30, 36].

E. Statistical Analysis Plan and Sample Size:

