Aim 1: Randomly missing item responses within measures will be handled via each measure's specific scoring protocol. Although minimal missing data are anticipated based on preliminary descriptive research using in-person data collection, missing responses for entire measures will not be assumed random and imputations will not be conducted. Quantitative data analysis will be conducted using SAS or IBM SPSS statistics software and performed by [name], with additional guidance from [name], as needed. Descriptive summaries of participant characteristics will be generated to inform the generalizability of our population estimates. Bootstrapped bias-corrected 95% confidence intervals will be generated around the observed sample proportions (categorical data), means (normally distributed continuous), and medians (skewed continuous). We have specified clinically important standards for demonstrating efficacy in Table 1. Frequency distributions summarizing the proportion of participants meeting the standards for demonstrating efficacy at 30-days follow-up will inform whether at least 80% met the standard. Furthermore, we will generate effect statistics with a 90% confidence interval to inform the powering of subsequent work. We will conduct tests of differences between pre and post-intervention ACP scores (e.g., Wilcoxon Signed-Rank Tests) as another preliminary test of the initial effect of the intervention on key outcomes. **Aim 2:** We will statistically and visually describe scores on each implementation measure and compare scores to the benchmarks decided on with our stakeholders as indicating adequate acceptability, appropriateness, and feasibility. **Sample Size Justification and Power:** The primary outcomes of the study are initial efficacy and acceptability, appropriateness, and feasibility of the ACP intervention. To optimize the information gleaned about the intervention, we have by design did not include any “control” condition and have not used a power analysis to motivate sample size. We are justifying our sample size based on the number of participants that we anticipate can reasonably enroll and complete all study measures during the funded period. Furthermore, 30 participants will suffice for generating relative stable parameter estimates of efficacy for informing future work. For the qualitative analysis, thirty interviews will more than suffice to reach data saturation, when no new themes emerge.

Table 2. Study Timeline Over Two Years

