Activity	2024				2025			
	Q1	Q2	Q3	Q4	Q1	Q2	Q3	Q4
Protocol development								
IRB approval/renewal								
Prepare study database								
Team training								
Purchase gift cards and distribute								
Intervention and data collection								
Data analysis								
Manuscript preparation and dissemination								
Grant development and submission								

Table 2. Key Outcomes

Variable (Measure)	Time Period	Aim	Purpose
ACP Processes: ACP Processes Scale (15-items, 5-point Likert scale (1 = almost never, 5 = almost always, participants rate how often they participate in different ACP processes. Higher summed scores indicate higher participation in ACP processes, e.g., I review my advance care documents so that I know what they say))	Baseline, 30-day follow-up	Aim 1	This scale assesses the frequency of participation in ACP processes. We hypothesize that at 30-day follow-up $\geq 80\%$ of the participants will endorse ACP process scores as anticipated compared with $<80\%$ at baseline. Possible scores: 15-75 Anticipated scores at baseline: <37 ; at 30-day follow-up: ≥ 37
ACP Values/Beliefs: ACP Values and Beliefs scale (7-item, 5-point	Baseline, 30-day	Aim 1	This scale assesses ACP misconceptions. We hypothesize

Likert (1=strongly agree, 5=strongly disagree, lower scores=fewer ACP misconceptions)	follow-up	
that at 30-day follow-up at least 80% of participants will hold ACP misconceptions as anticipated compared with <80% at baseline.
 
Possible scores: 7-35
 
Anticipated scores at baseline: <28; at 30-day follow-up: ≥ 28

ACP Actions: ACP Stages of Change Scale (6-items, 5-point Likert (0=no, not at all, 4=yes, I've done that months or years ago, higher scores on individual items and overall=higher ACP participation)	Baseline, 30-day follow-up	
Aim 1
 
This scale indicates the stage of change (precontemplation to maintenance) that each participant is in for the six core ACP actions/behaviors. We hypothesize that at 30-day follow-up $\geq 80\%$ of participants will report ACP actions as anticipated compared with <80% at baseline.
 
Possible overall scores: 0-24
 
Anticipated overall scores at baseline: <14, at 30-day follow-up: ≥ 14
 
Possible scores for individual ACP actions: 0-4
 
Anticipated individual scores at baseline: 0-2, at 30-day follow-up: 3-4

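### The 80% efficacy statement counts 30-day status only, so participants already at the standard at baseline count as successes; report the baseline-by-follow-up cross-table and paired change beside it (minor)

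*Combined protocol and SAP*

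**What the plan says.** Section E (Aim 1) announces the standards with "We have specified clinically important standards for demonstrating efficacy in Table 1" and says that the proportion "meeting the standards for demonstrating efficacy at 30-days follow-up will inform whether at least 80% met the standard". The standards are in fact in Table 2. Key Outcomes; Table 1 is the conversation checklist.

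For Actions, that table gives a total-score standard ("Anticipated overall scores at baseline: <14, at 30-day follow-up": at least 14, on a 0-24 range) and a per-action one ("Anticipated individual scores at baseline: 0-2, at 30-day follow-up: 3-4"). The top item score is described as "done that months or years ago, higher scores on individual items and overall=higher ACP participation". The hypothesis is that at least 80% "of participants will report ACP actions as anticipated compared with <80% at baseline". Processes (at least 37 at follow-up) and Values/Beliefs (at least 28) follow the same pattern.

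Section E also states: "We will conduct tests of differences between pre and post-intervention ACP scores", with the Wilcoxon signed-rank test as the example. It plans effect statistics with 90% confidence intervals for powering later studies. D3 excludes people who already have a completed advance directive and sets no limit on any baseline ACP score.

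**The concern.** H1 is about change: fewer misconceptions, more ACP processes, more ACP actions. The 80% statement measures something else, namely where people stand at 30 days. The baseline values in Table 2. Key Outcomes are labelled as anticipated; they are neither entry criteria nor counting rules. A participant who starts at or above the cut-off and stays there counts towards the 80% exactly as a new achiever does.

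For Actions this is built into the scale. The top item score is for actions taken months or years earlier, so at a visit 30 days after the intervention it will generally describe something done before the study.

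Initial efficacy is named as a primary outcome. The same reported 24 of 30 could reflect quite different amounts of change, and the statement alone does not show which.

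**Working it through.** **Inputs.** n = 30 and the 80% benchmark (section E); Actions cut-off 14 of 24 (Table 2. Key Outcomes); exclusion of completed directives only (D3); pilot rates of 7/15, 6/15 and 3/15 for three single actions (section C). The number already at the standard, *b*, is not in the documents and is an assumption throughout.

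**1. Benchmark as a count.** 0.80 × 30 = 24, if all 30 have a 30-day score. The plan derives no sample size or power from it, so there is no further figure to reproduce.

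**2. Can an eligible person start at 14 or more?** Yes. With the advance-directive action at 0, three other actions at 4 and one at 2 give 3 × 4 + 2 = 14.

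**3. Does the group clause prevent it?** No. 23/30 = 76.7% is below 80% at baseline. One new achiever gives 24/30 = 80%, and the hypothesis is met. At 24/30 at baseline the section E count is met with no change at all, although the Table 2 baseline clause then fails.

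**4. Size.** Suppose *b* participants start at the standard and none falls below it. Conversion needed among the rest = (24 − b)/(30 − b). Paired change = (24 − b)/30. Intervals are 95%: Clopper-Pearson for conversion; Newcombe for paired proportions, continuity-corrected, for the change. With 24 − b changes in one direction and none in the other, exact McNemar p = 2 × 0.5^(24 − b), capped at 1.

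| b (assumed) | Conversion needed | Paired change, points | McNemar p |
|---|---|---|---|
| 0 | 24/30 = 80% (61 to 92) | 80 (59 to 91) | <0.0001 |
| 3 | 21/27 = 78% (58 to 91) | 70 (47 to 82) | <0.0001 |
| 6 | 18/24 = 75% (53 to 90) | 60 (37 to 74) | <0.0001 |
| 12 | 12/18 = 67% (41 to 87) | 40 (20 to 56) | 0.0005 |
| 23 | 1/7 = 14% (0.4 to 58) | 3 (−7 to 14) | 1.0 |

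The last row is the arithmetic limit, not an expectation.

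**5. What the pilot says about b.** Little. The exact 95% intervals are 21-73% for 7/15, 16-68% for 6/15 and 4-48% for 3/15. These are single actions. All three at the maximum total 3 × 4 = 12, below 14, so they do not estimate the share at or above 14. They would bear on the result only if the per-action 3-4 bands were the standard and the pilot questions matched scale items, which the documents do not state. On those assumptions, doubling the counts to n = 30 gives 14, 12 and 6 already there, and needed conversions of 10/16 = 62.5%, 12/18 = 66.7% and 18/24 = 75%.

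**The case against.** The case on the other side is substantial.

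- **Baseline is not hidden.** Testing the Table 2 hypothesis requires the baseline proportion at the same cut-off, so a reader would see 23/30 beside 24/30. This stands. What remains is that the two proportions are not split into new achievers, those already there and those who fell back.
- **Change is analysed elsewhere.** Section E plans pre-post tests, and its effect statistics with 90% intervals are the stated basis for powering later work. This also stands, although the effect statistic is not named. A later study need not be powered from the 80% count, and no go/no-go decision rests on it.
- **At moderate b the change would still show.** With 6 or 12 already at the standard, the paired change is 60 or 40 points with p of 0.0005 or less. Only the arithmetic limit gives p = 1.0.
- **Nothing shows that b is large.** People with a completed directive are excluded, and a total of 14 needs several actions at advanced stages.

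A reader might infer from the pilot's 20-47% that a large part of any reported 80% will predate the study. The documents do not support this: those rates concern single actions, in 15 residents, 2 of whom apparently had a directive and would be ineligible.

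A reader might also conclude that the 80% criterion should move to participants below the standard at baseline. That would apply a bar the sponsor never set (with b = 6, 20/24 instead of 18/24) and would put regression to the mean into the headline. Assuming no true change, bivariate normal scores and a test-retest correlation of 0.6-0.9, about 6-13% of those below the cut-off would pass at 30 days if 20% pass at baseline, and 12-24% if 40% do. Under the same assumptions the expected paired change among all participants is zero.

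**Conclusion.** The point holds as a minor reporting gap that applies to all three scales. The 80% statement describes status at 30 days and cannot by itself support an increase; the group-level baseline clause and the separate analyses of change do not alter what it counts. The size depends entirely on an unknown baseline share. It is trivial if 3 of 30 start at the standard (78% conversion needed instead of 80%) and visible if 12 of 30 do (67%). These figures assume complete follow-up and no participant dropping below the cut-off. The documents do not support saying that the efficacy result will be misleading, or that the benchmark itself is wrong.

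Two ambiguities must be settled before the count can be made. The plan does not say whether the Actions statement uses the total of at least 14 or the 3-4 item bands. For Values/Beliefs, the table says that lower scores mean fewer misconceptions, yet the follow-up standard is a score of 28 or more; read literally, meeting it means holding more misconceptions.

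**What to change.** Keep the 80% count among all participants as the sponsor's benchmark. Add to section E, for each of the three scales:

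> The baseline-by-30-day cross-table of meeting the standard (missing 30-day scores in their own column) and the paired change in proportion with its confidence interval, among participants with both scores, will be reported beside the 80% statement, and the statement will be interpreted as an increase only together with that paired change.

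Name the confidence level, since section E uses both 95% and 90%. Conversion among those below the standard at baseline may be shown descriptively with a regression-to-the-mean caveat, not as a new 80% criterion.

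In the same edit:
- state which Actions standard the 80% statement uses;
- reconcile the Values/Beliefs scoring direction with its cut-off before any cut-off is applied;
- point the Table 1 reference in section E to Table 2. Key Outcomes, by full title, because the study timeline is also numbered Table 2.

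Cost: a few sentences and slightly more reporting, from data both questionnaire visits already collect. The message may be less favourable. The document is dated November 2025; if outcome data have already been seen, the addition must be labelled post hoc.

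### ACP Values/Beliefs: the stated score direction contradicts the success cut-off, so it is unclear whether a follow-up score of 28 or more is improvement

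*Combined protocol and SAP*

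**What the plan says.** The Key Outcomes table (the second table numbered 2, at the end of Section E) describes the ACP Values/Beliefs scale as seven items on a five-point Likert scale, with "1=strongly agree, 5=strongly disagree, lower scores=fewer ACP misconceptions". The same row says "This scale assesses ACP misconceptions" and gives a possible range of 7 to 35. Its cut-off reads "Anticipated scores at baseline: <28", followed by 28 or more at the 30-day follow-up. The row's hypothesis is that 80% or more of participants "will hold ACP misconceptions as anticipated compared with <80% at baseline".

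H1 in Section A (Aim 1) predicts that misconceptions will go down after the intervention.

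Section E uses the cut-offs as the efficacy criterion: frequency tables of participants "meeting the standards for demonstrating efficacy at 30-days follow-up will inform whether at least 80% met the standard". Its sample-size paragraph states: "The primary outcomes of the study are initial efficacy and acceptability, appropriateness, and feasibility of the ACP intervention". Section E also plans pre-post tests, with Wilcoxon signed-rank as an example, and effect statistics with 90% confidence intervals to help power later work.

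**The concern.** If lower scores mean fewer misconceptions, H1 requires scores to fall. The efficacy standard in the same row requires them to rise. One of the three statements must be wrong, and the plan does not show which. Two readings remain:

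1. **The label is wrong.** The items state misconceptions and answers are summed as given. Disagreement then earns 5 points, high totals are favourable, and 28 or more agrees with H1.
2. **The label is right.** Either the items state correct beliefs, or misconception items are reverse-scored. Low totals are then favourable, and the standard counts the wrong end of the scale.

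At stake is the success rule for one of the three Aim 1 efficacy scales, and whether the pre-post change is reported as benefit or harm. If the direction is chosen only after the scores have been seen, that choice could decide the result.

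**Working it through.** **Inputs.** From the Key Outcomes table: 7 items scored 1 to 5; range 7 to 35; cut-off 28; standard of 80%. From Section A: n = 30 and the direction of H1. The plan has no power calculation to reproduce.

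**Range.** 7 × 1 = 7 and 7 × 5 = 35, which agrees with the table. That gives 35 − 7 + 1 = 29 possible totals.

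**Position of the cut-off.**
- Mean item answer at 28: 28/7 = 4.0, one step short of strong disagreement.
- Position on the range: (28 − 7)/(35 − 7) = 21/28 = 75%, so 28 opens the top quarter.
- Totals that pass: 28 to 35, which is 8 of 29.
- Mirror image: 7 + 35 − 28 = 14, a mean item answer of 14/7 = 2.0. Totals 7 to 14 are also 8 of 29.
- Simple flip to below 28: totals 7 to 27, which is 21 of 29. This is the range the table already expects at baseline.

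**Direction in the three Aim 1 rows.**

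| Scale | Stated direction | Cut-off, baseline to 30 days | Agree? |
|---|---|---|---|
| Processes | "Higher summed scores indicate higher participation in ACP processes" | below 37 to 37 or more (rise) | Yes |
| Actions (overall) | "higher scores on individual items and overall=higher ACP participation" | below 14 to 14 or more (rise) | Yes |
| Values/Beliefs | lower is better | below 28 to 28 or more (rise) | No |

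Only the Values/Beliefs row conflicts, so this is not a convention of the table.

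**Effect on the 80% standard**, assuming all 30 complete follow-up. The standard needs 0.80 × 30 = 24 participants. Take a result that just passes as written:
- 28 or more: 24/30 = 80%, pass.
- Below 28: 30 − 24 = 6, so 6/30 = 20%, fail.
- 14 or less: at most 6/30 = 20%, fail.

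**Two constructed data sets** (assumed, for illustration), with everyone at 20 at baseline:

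| Follow-up | 28 or more | 14 or less | Mean change |
|---|---|---|---|
| 24 rise to 30, 6 stay at 20 | 80% | 0% | 24 × 10/30 = +8.0 |
| 24 fall to 12, 6 stay at 20 | 0% | 80% | 24 × (−8)/30 = −6.4 |

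Each data set passes in one direction and fails in the other.

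**Anything that settles it?** No item wording is given. Section E mentions scoring protocols only for items missing at random. The row's hypothesis sentence merely points back to the disputed cut-off.

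**The case against.** The strongest reply is that the numerical rule is explicit: an analyst following the text counts 28 or more. The anchors, the description of the scale as measuring misconceptions, H1 and the rising cut-off all fit together if the items state misconceptions and are summed unreversed. Only a short label is then out of place, and the right participants are counted. This is at least as plausible as the alternative. It cannot be confirmed from the documents, however, because reverse-scored or mixed items would change the answer. Nor would the wrong label be harmless. An analyst who reversed the totals to honour it (new total = 42 − raw total) and then applied 28 or more would count raw totals of 14 or less, which on that reading are the participants with the most misconceptions.

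It is also fair to say that the consequences are limited. This is an unpowered single-arm pilot, the 80% comparison is descriptive, and no go/no-go decision is attached to it. A two-sided Wilcoxon p-value and the absolute effect size do not depend on the direction, although the plan does not state sidedness. These points stand. They limit the harm but do not remove the contradiction from a success criterion for a primary outcome.

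**Conclusion.** The concern holds. The label, the cut-off and H1 for ACP Values/Beliefs are mutually inconsistent, and nothing in the documents resolves them.

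The size depends on which element is wrong. If it is the label, no result reverses and the correction is one of wording. If it is the cut-off, the rule rewards the top 25% of the misconception range, and a bare pass of 80% becomes 20% or less. The 24/30 and 6/30 figures assume complete follow-up and a result exactly at the threshold; they illustrate the reversal and do not predict data. The sample size is unaffected. What is unclear in the pre-post analysis is whether the sign of the change means benefit or harm, and that sign passes into the effect statistics intended for later studies.

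**What to change.** Before scoring, check the item wording and scoring key of the cited instrument, and state one direction, including any reverse scoring. Then do one of the following:

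- **(a)** Change the label so that higher scores mean fewer misconceptions, and keep 28 or more. This needs no new number.
- **(b)** Keep the label and reverse the inequality, with a cut-off that the sponsor justifies, and revise the anticipated baseline score to match. The documents support no particular value: below 28 is only a flip, and 14 is only the arithmetic mirror.

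Reword the row's hypothesis so that 80% or more are expected to hold few misconceptions. Add a sentence to Section E saying which sign of the pre-post change and of the effect statistic means improvement. If scoring has already begun, record the direction used and when it was decided.

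The cost is one table row and one SAP sentence after a look at the scoring key. Data collection does not change.
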